## **BASELINE ASSESSMENT**

### **BASELINE VARIABLES**

- Baseline Target Toenail Variables
- Prior Treatment Approaches
- Concomitant Medications And Therapies
- Notation of any other toenail(s) on the target foot that appear to be infected with onychomycosis.
- Subject Demographics

### **CLINICAL AND OUTCOME EVALUATIONS**

- Nail Etching
- Photographic Documentation
- Measurement of mm of Clear Nail
- Percentage Of Clinical Onychomycosis Involvement Determination

## **TREATMENT ADMINISTRATION PHASE**

### **GENERAL ASSESSMENT CONDITIONS**

Subjects must agree to not partake in any non-study treatment(s) for toenail onychomycosis (including oral medications and nail lacquer, non-alternative therapies such as acupuncture and home remedies), or to use any toenail cosmetics throughout the course of study participation.

### **TREATMENT ADMINISTRATION PROTOCOL**

- The treatment administration phase of the study will last 11 months, comprised of an initial weekly treatment administration phase followed by an every two month maintenance treatment administration phase.
- The treatment administration phase of the study will commence on the same day as the Baseline Assessment visit, following completion of all activities related to the Baseline Assessment visit.
- The initial weekly treatment administration phase will last three weeks and involve four in-office treatment administrations with the Erchonia® LunulaLaser™, each one week (7 days) apart (i.e. Days 1, 8, 15 and 22).
- The maintenance treatment administration phase involves the subject returning to the test site one time every eight weeks (2 months) following the final weekly treatment administration for a single maintenance treatment administration with the Erchonia® LunulaLaser™ (i.e. end of months 3, 5, 7, 9 and 11).
- Each treatment administration lasts 12 minutes.
- Each treatment administration is administered by the study investigator at the test site.

The treatment administration protocol for each of the Erchonia® LunulaLaser™ laser treatment administration is as follows:

1. The subject is seated comfortably with the LunulaLaser™ placed on the floor in front.
2. The subject is fitted with the safety glasses.
3. The subject places the foot with the infected great toenail to be treated in this study on the treatment platform inside the Erchonia LunulaLaser™ laser device – heel on the back, toes on the front platform under the laser output heads, as shown in the figure below.

4. The Erchonia LunulaLaser™ is activated such that the laser light is directed at the great toenail at a distance of approximately 4 inches above the toenail.
5. The dual wavelengths of 405 nm and 635nm are activated simultaneously for 12 minutes of total treatment administration time.

By design of the device, it is not possible for the subject to move the foot's position to any significant degree that would impact the intended exposure to the laser procedure, particularly considering that the laser beam is designed to cover the entire treated toe region. The exception would be if the subject withdrew his or her foot entirely from the laser device mid-treatment administration, in which case, the foot would be re-inserted at once and the remaining minutes of exposure completed such that the total maximum exposure time in one session would not ever exceed the pre-determined 12-minutes. If the subject was unable or refused to re-insert his or her foot for any reason, the subject would be disqualified from further study participation at that time.

6. The subject removes his or her foot from the Erchonia LunulaLaser™.
7. The laser treatment administration is complete.
8. The subject removes the safety glasses, and the treatment procedure administration protocol is completed.

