#### Compensation

A subject will not be offered money or any other form of compensation to participate in the clinical study. However, he or she will also not be charged for the cost of the study treatments with the Erchonia® LunulaLaser™, the cost of the mycological lab testing or for the cost of any other directly-related evaluations or measurements that occur as part of his or her participation in the study.

Sample size

There will be 66 qualified subjects/great toenails enrolled in this clinical study across three test sites, approximately 22 subjects/great toenails per test site.

Rationale for sample size

The sample size of 66 subjects/great toenails was calculated based upon the 95% one-sided confidence interval (i.e. lower bound only) around the observed response rate of 70% being  $\geq$  50% (56%) yielding a pre-determined final sample size of 60 subjects/great toenails. From here, it is anticipated that about one-twelfth of subjects overall may withdraw or be terminated from the study prior to completion for various reasons. Therefore, the following formula is used to determine the final needed starting sample size for each procedure arm:

Final sample size = sample size  $\times$   $1/(1-d)$ ; where  $d$  = # expected dropouts/# subjects enrolled

Final sample size =  $60 \times 1/(1-0.082)$

Final sample size =  $60 \times 1/0.917 = 60 \times 1.091 = 66$  subjects

Therefore, a minimum starting sample size of 66 subjects is needed to insure that a sufficient number remains at the end of the treatment administration phase (60 subjects), assuming a drop-out rate of around one-twelfth, for a positive study outcome to be considered statistically valid, clinically meaningful and representative of the general population being sampled.

Subject Recruitment Advertisement

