## Toenail Fungus Research Study

This study is to see if the Erchonia LunulaLaser™, a non-invasive device that uses low-level laser light to grow new nail in toenails with toenail fungus can help to get rid of the fungus in the toenail altogether.

The study involves 12 visits to a test site over about 14 months.

Please contact  
<Test Site/PI name> at <phone#> or  
<e-mail> for details.

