## **SUBJECT DAILY DIARY**

On each day of the study, the subject will record the following measures in a Daily Diary supplied by the investigator at the test site on the day of the first treatment administration.

- ✓ Compliance with abstinence from other (non-study) treatments for toenail fungus
- ✓ Compliance with abstinence from the use of nail cosmetics on study toes
- ✓ Any changes in medication use and/or therapies engaged in from those reported at baseline evaluation
- ✓ Potential perceived adverse events, as described in the 'Adverse Events' evaluation tool listed below.
- ✓ Any study-related comments, if and as desired

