## **ADVERSE EVENTS EVALUATION**

Prior clinical trials applying the Erchonia® LunulaLaser™ to toenail onychomycosis have not yielded any adverse events or reactions. Numerous additional clinical trials applying Erchonia® low level laser for various different indications have also not yielded any adverse events or reactions. Therefore, it is unlikely and not expected that any adverse events will result from implementation of this clinical study protocol.

However, potential adverse events that may feasibly occur from application of the Erchonia LunulaLaser™ include, but are not necessarily limited to: skin irritation, discoloring, rash, indentations and re-infection.

Adverse events evaluation will include formal evaluation of the treatment area and surrounding skin area by the investigator at each subject test site visit as well as review of any potential events reported or recorded in the Subject Daily Diary by the subject. Adverse events evaluation will be conducted for all toenails on the foot with the study treated toenail.

Any and all observation(s)/report(s) of potential adverse events, whether observed by the investigator or reported by the subject, whether anticipated or unanticipated, will be recorded on the Adverse Events case report form and subsequently evaluated by the investigator for its relation to the study procedure and whether or not any corrective action needs to be taken. All potential adverse events recorded will be appropriately reported to the governing IRB, as applicable.

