##### ***CLINICAL CRITERIA EVALUATION***

*Inclusion Criteria:* The subject will continue to the Baseline Assessment phase if all of the following clinical inclusion criteria are satisfied:

- Visual clinical presentation of onychomycosis in the target great toenail is distal subungual onychomycosis (DSO), visualized as a nail with normal surface texture and thickness but variable "bays" of white nail that extend from the distal nail tip proximally into the area of the nail bed
- Clinical involvement of onychomycosis in the target toenail is between 20%–50%
- Subject is willing and able to refrain from employing other (non-study) treatments (traditional or alternative) for his or her toenail onychomycosis throughout study participation.
- Subject is willing and able to refrain from the use of nail cosmetics such as clear and/or colored nail lacquers throughout study participation
- Male or female
- 18 years of age or older

**Exclusion Criteria:** The subject's participation in the study will end at this time if any one or more of the following clinical exclusion criteria are satisfied:

- Visual clinical presentations of onychomycosis in the target great toenail that are inconsistent with the clinical presentation of distal subungual onychomycosis (DSO), in whole or in part (i.e. indicative of mixed etiology); specifically visual clinical presentations consistent with one or more of the following:
  - *Proximal subungual onychomycosis (PSO):* visualized as a white discoloration below the nail plate at the base of the nail, near the lunula. The distal nail retains normal appearance and texture. PSO involves infection near the matrix, deep to the nail. It may be associated with trauma to the nail or to immune compromise
  - *Superficial white onychomycosis (SWO):* visualized by the appearance of a white coating on the nail surface that can be eliminated by filing or buffing the surface of the affected portion of the nail
  - *Complete dystrophy:* Nails which are 100% dystrophic are manifested by yellowing and thickening of the entire nail unit
  - *Other nail changes:* Nails that visually present with changes that appear as parallel lines, small pinpoint depressions, brown spots, black or brown linear streaks, complete yellowing of all nails without textural change, green debris below the nail, or notches in the nail margin
- Less than 2mm clear (unaffected) nail plate length beyond the proximal fold

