#### **AT EACH TREATMENT ADMINISTRATION AND EVALUATION VISIT**

- Adverse Events Evaluation

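### A subject who cannot or will not resume an interrupted laser session is removed from the whole study, so scheduled safety checks and the Month 12 and Month 14 observations are lost

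*Combined protocol and SAP*

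**What the plan says.** Under Treatment Administration Protocol, a subject who withdraws the foot completely during a session should put it back at once and finish the remaining minutes, within the 12-minute total. The plan treats this as an exceptional event. It then adds that, if the subject is "unable or refused to re-insert his or her foot for any reason, the subject would be disqualified from further study participation at that time". An interruption that is resumed has no further consequence.

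Follow-up is attached to visits and to participation:

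- Adverse Events Evaluation provides for "formal evaluation of the treatment area and surrounding skin area by the investigator at each subject test site visit", together with review of the subject's diary. The Study Evaluation Timeline schedules it under the heading "AT EACH TREATMENT ADMINISTRATION AND EVALUATION VISIT".
- The Subject Daily Diary runs from the first treatment day to study end.
- Photographs, clear-nail measurement, percentage involvement and culture are taken at the fourth weekly treatment, at Months 3, 5, 7, 9 and 11, at the Month 12 endpoint, and two months after that.
- The Adverse Events section under Safety and Confidentiality also allows events to be recorded at other times when necessary, but it schedules no contact.

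In the Statistical Analysis Plan, the primary methods section includes everyone with a valid baseline visit in the intent-to-treat set, scores subjects who drop out or are lost to follow-up as failures, and fills missing values by last observation carried forward (LOCF). It does not mention disqualified subjects. The Safety Analyses section uses all consented and enrolled subjects and assesses incidence, frequency and severity.

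**The concern.** The rule treats stopping treatment and leaving the study as one event. They need not be: ending the laser does not prevent a skin check, a photograph or a culture. Because the rule applies whatever the reason, it covers a subject who stopped because of pain or a skin reaction. That is a subject in whom one would want to know whether the effect persisted, worsened or was followed by another. There is no control arm to put a low event count in context, and the sponsor expects no adverse events, so single observations carry weight.

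On efficacy, the Month 12 visit is lost in every case. The three secondary endpoints at week 52 (less than 10% of the nail affected, negative culture, and change in healthy nail) are then not observed for that subject.

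**Working it through.** **Visits.** Sessions 1 to 4 fall on Days 1, 8, 15 and 22, and sessions 5 to 9 at Months 3, 5, 7, 9 and 11 (Treatment Administration Protocol). The Month 12 endpoint visit and the post-treatment visit two months later (Month 14) follow. Adverse-event evaluations therefore number 4 + 5 + 2 = 11. As a check, the recruitment advertisement says "The study involves 12 visits to a test site over about 14 months", and 12 less one qualification visit is 11. Post-baseline nail and culture assessments begin at session 4: 1 + 5 + 2 = 8.

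**Losses after a stop at session k.** Adverse-event evaluations lost = 11 − k. Nail and culture assessments lost = 8 for k = 1 to 3, and 11 − k from k = 4. This assumes that the assessments due at visit k were done; if the nail and culture assessments were not, one more of them is lost from k = 4 on.

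| Stop at session | Time | Adverse-event evaluations lost (of 11) | Nail/culture assessments lost (of 8) |
|---|---|---|---|
| 1 | Day 1 | 10 | 8 |
| 2 | Day 8 | 9 | 8 |
| 3 | Day 15 | 8 | 8 |
| 4 | Day 22 | 7 | 7 |
| 5 | Month 3 | 6 | 6 |
| 6 | Month 5 | 5 | 5 |
| 7 | Month 7 | 4 | 4 |
| 8 | Month 9 | 3 | 3 |
| 9 | Month 11 | 2 | 2 |

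In time, about 14 months of follow-up are lost after a stop at session 1, about 13 after session 4, and 14 − 11 = 3 after session 9. Follow-up for re-infection is lost only from session 4 on, because no post-baseline culture is due before then.

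**Primary endpoint.** Scoring one subject as a non-responder lowers the clinical cure rate by at most 1/66 = 1.5 percentage points, against the device. The mycological criterion is a proportion among clinical responders, so such a subject leaves its denominator and the shift can go either way. The clinical criterion needs 0.70 × 66 = 46.2, that is 47 responders. Taking one subject out of 48 or more moves the mycological proportion by at most 1/48 = 2.1 points.

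**LOCF against failure scoring.** For stops at sessions 1 to 3, the last clear-nail value is baseline, so LOCF gives no change. From session 4 there is a post-baseline value to carry forward. A subject disqualified late with a clear nail and a negative culture could then be argued to be a responder under LOCF, but a failure if disqualification counts as dropping out. The second reading is the more natural one, but the text does not state it.

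**Frequency.** The plan gives none for this event. The nearest figure is attrition for all causes: Rationale for sample size expects that "about one-twelfth of subjects overall may withdraw or be terminated from the study prior to completion for various reasons". Its own calculation reproduces: 60 / (1 − 1/12) = 65.45, rounded up to 66, which allows 66 − 60 = 6 losses. That is an allowance for every route out of the study and says nothing about how many take this one.

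**The case against.** The strongest case is that little is lost. An event serious enough to make someone pull out the foot happens at a treatment visit, where evaluation is already required, so that subject enters the incidence count. A reader might infer that the rule hides the very events that cause the stop, or that adverse-event incidence must come out too low. The documents do not support this. Only persisting, later or different effects can be missed. Nor is it peculiar to this rule that a subject examined once counts in the safety denominator like one examined 11 times; that is true of any dropout.

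A reader might also infer that the change in healthy nail can have no value for such a subject. That does not follow either: clear nail is measured at baseline, and LOCF, if it extends to secondary endpoints, would supply a figure. The LOCF and failure rules stand in the section on primary methods, so their reach is not explicit. What remains is that the value would be imputed, not measured.

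The event may also be very rare. The exposure lasts 12 minutes and generates no heat, the plan reports no adverse events in prior trials of the device, and the rule needs both a withdrawal and a failure to resume. Follow-up after termination might be covered in the appendices on case report forms, consent, monitoring or investigator responsibilities, which are not in the text reviewed.

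These points limit the size of the concern. They do not remove it: the rule as written ends participation, and permission to record events at other times is no substitute for a scheduled examination.

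**Conclusion.** The point holds as a minor one, mainly about safety follow-up. For each affected subject, between 2 and 10 of the 11 adverse-event evaluations and between 2 and 8 of the 8 nail and culture assessments are given up, and Months 12 and 14 are always among them. The number of such subjects is unknown and may be zero.

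It would be tempting to read the rule as a threat to the primary result. The documents do not support that: the subject stays in the intent-to-treat set, the natural score is non-responder, and the cost is at most 1.5 points of clinical cure per subject, against the device. Only the unstated precedence of failure scoring over LOCF leaves a small opening the other way, and one sentence closes it.

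The conclusion assumes that disqualification means what it says, that nothing in the unseen appendices restores follow-up, and that assessments due at the interrupted visit are completed.

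**What to change.** In Treatment Administration Protocol, replace disqualification from the study with permanent discontinuation of laser treatment. Record the minutes delivered and the reason. Unless consent is withdrawn, keep the scheduled adverse-event evaluations and, if the subject agrees, the Month 12 and post-treatment nail and culture assessments.

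In the primary methods section, name these subjects as non-responders in the primary analysis, so that LOCF cannot turn one into a responder. Use their observed Month 12 results descriptively only, flagging any other antifungal treatment.

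One consequential edit is needed. Entry requires willingness to "refrain from employing other (non-study) treatments (traditional or alternative) for his or her toenail onychomycosis throughout study participation", and General Assessment Conditions repeats that "Subjects must agree to not partake in any non-study treatment(s) for toenail onychomycosis". A subject kept in follow-up without laser treatment should be released from both. Other treatment can be captured at visits, or in the diary if the subject continues it, since the diary already asks for "Any changes in medication use and/or therapies engaged in from those reported at baseline evaluation". The Per-Protocol set needs no change, because it is already limited to subjects who completed the full protocol.

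The cost is a few sentences, an exception to the abstinence rules and one case report form entry. The sample size stays at 66, since the one-twelfth allowance already covers terminations. The downsides are continued visits for a few subjects and later efficacy data that may be confounded by other treatment, which is why the primary score stays non-responder.

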### **STUDY EVALUATION TIMELINE AND MEASURES**

The evaluation time points and associated measures (as outlined in the STUDY TEST BATTERY section above) to be evaluated during the course of this study are as follows:

#### **DAILY COMMENCING ON THE DAY OF THE FIRST TREATMENT ADMINISTRATION THROUGH TO STUDY END**

- Subject Daily Diary

#### **AT EACH TREATMENT ADMINISTRATION AND EVALUATION VISIT**

- Adverse Events Evaluation

#### **AT EACH TREATMENT ADMINISTRATION VISIT COMMENCING WITH THE FOURTH WEEKLY TREATMENT ADMINISTRATION (END OF WEEK 4, MONTHS 3, 5, 7, 9, AND 11)**

- Photographic Documentation
- Measurement of mm of Clear Nail
- Percentage of Clinical Onychomycosis Involvement Determination
- Mycological Evaluation: InTray™ DM Culture

#### **STUDY ENDPOINT EVALUATION: 12 MONTHS FOLLOWING THE INITIAL TREATMENT ADMINISTRATION**

- Photographic Documentation
- Measurement of mm of Clear Nail
- Percentage of Clinical Onychomycosis Involvement Determination
- Mycological Evaluation: InTray™ DM Culture

#### **TWO MONTHS AFTER STUDY ENDPOINT EVALUATION POST-TREATMENT EVALUATION**

- Photographic Documentation
- Measurement of mm of Clear Nail
- Percentage of Clinical Onychomycosis Involvement Determination
- Mycological Evaluation: InTray™ DM Culture

### **TABLE OF SUBJECT EVENTS**

The following table provides a progressive summary of subject events throughout this study.

PRE-TREATMENT ACTIVITIES
STUDY QUALIFICATION EVALUATION 

➤ A potentially well-suited and interested candidate for participation in the study attends the investigator's office.

➤ The investigator reviews the informed consent form with the candidate.

➤ If the candidate continues to be interested and voluntarily signs the informed consent form, Study Qualification Evaluation is performed: Mycological Evaluation followed by Clinical Evaluation criteria.

➤ A fully qualified subject progresses to the Baseline Assessment phase.

BASELINE ASSESSMENT
BASELINE VARIABLES 

➤ Baseline Target Toenail Variables

➤ Prior Treatment Approaches

➤ Concomitant Medications and Therapies

➤ Notation of all infected toenails on the target foot

➤ Subject Demographics

CLINICAL AND OUTCOME EVALUATIONS 

➤ Nail Etching

➤ Photographic Documentation

➤ Measurement of mm of Clear Nail

➤ Percentage of Clinical Onychomycosis Involvement Determination

TREATMENT ADMINISTRATION PROTOCOL 
Each participant receives 4 12-minute treatment administrations with the Erchonia® LunulaLaser™ over 4 consecutive weeks, each 7 days apart, followed by one treatment every two months thereafter. Each treatment is administered at the test site.

### STUDY EVALUATION TIMELINE AND MEASURES

#### **DAILY COMMENCING ON THE DAY OF THE FIRST TREATMENT ADMINISTRATION THROUGH TO STUDY END**

- Subject Daily Diary

#### **AT EACH TREATMENT ADMINISTRATION AND EVALUATION VISIT**

- Adverse Events Evaluation

#### **AT EACH TREATMENT ADMINISTRATION AND EVALUATION VISIT COMMENCING WITH THE FOURTH WEEKLY TREATMENT ADMINISTRATION**

- Photographic Documentation
- Measurement of mm of Clear Nail
- Percentage of Clinical Onychomycosis Involvement Determination
- Mycological Evaluation: InTray™ DM Culture

